11.3.3 Slit Lamp Biomicroscopy

Slit Lamp biomicroscopy assessments will evaluate corneal edema, ciliary flush, bulbar conjunctival injection. The assessments for the study eye will be performed from Screening through EOMS. The assessments for the non-study eye will be performed at Screening and EOMS. The following grades will be used for the assessments.

Grade	Description
0	Absent
1	Mild
2	Moderate
3	Severe

The number and percentage of subjects in each grade category of the assessments will be tabulated by treatment group at each post-surgery scheduled visit through EOMS for the study eye.

A shift table of assessment grades from Screening to EOMS for both eyes will be presented by treatment group.

In addition, the non-study eye lens status (phakic, non-phakic or pseudophakic) will be assessed at Screening. The number and percentage of subjects in each status category will be tabulated.

The data of the biomicroscopy assessments for safety evaluation will be presented in a data listing.

11.3.4 Dilated Indirect Ophthalmoscopy

A dilated indirect ophthalmoscopic examination will be performed at Screening and EOMS for both eyes to evaluate the vitreous, retina, macula, choroid, and optic nerve with cup/disc ratio and will note normal/abnormal findings.

A shift table from Screening to EOMS for each ophthalmoscopic parameter, except for the cup/disc ratio, will be presented by treatment group for both eyes. The cup/disc ratio and change from Screening to EOMS will be summarized descriptively for both eyes.

For the non-study eye only, when the non-study eye is reported as 'Phakic' at the Screening Visit, the lens will be assessed for the presence or absence of a cataract. If a cataract is present, it will be classified as Nuclear, Cortical, or Posterior Subcapsular and graded using the guidance provided in the [protocol Appendix B](#). A shift table of the cataract grade from Screening to EOMS for each cataract location will be presented by treatment group.

The data of the dilated indirect ophthalmoscopic examinations will be presented in a data listing.

11.4 Corneal Endothelial Cell Parameters in the Endothelial Cell Sub-study

Corneal endothelial cell parameters will be measured by a central reading center from the images obtained using a specular microscope. Measurements of corneal endothelial cell density (units: cell/mm²), percent hexagonality (units: % of cells with hexagonal shape) and coefficient of variation in the sizes of the endothelial cells (units: % variation in size between endothelial cells) will be performed for the study eye at Visit 1/Screening, Visit 6/POD22, Visit 7/POD85 and Early Termination Visit prior to EOSS in the subjects participating in the Sub-study. The measurements of endothelial cell parameters will also be performed at Screening for the non-study eye.

The corneal endothelial cell parameter data for the study eye will be summarized at each assessment visit by treatment group. The mean change from Screening to Visit 7/POD85 with associated 95% CI for the study eye will be tabulated for the three parameters by treatment group, as appropriate. The percent change from Screening to Visit 7/POD85 for corneal endothelial cell density will also be summarized.

The corneal endothelial cell parameter data will be presented in a data listing, including the measurements of endothelial cell parameters at Screening for the non-study eye.

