3.0 STUDY DESIGN

3.1 STUDY DESIGN OVERVIEW

This Phase 3 study will evaluate APP13007 in comparison to the matching vehicle placebo in a randomized, parallel-group, double-masked fashion. The subjects will have undergone routine cataract surgery on Day 0 of the study and will be assessed the next day (POD1) after uncomplicated surgery for eligibility for randomization to study treatment. The study comprises the Main Study and the Endothelial Cell Sub-study. All randomized subjects (approximately

370) will participate in the Main Study. The Endothelial Cell Sub-study will comprise a subgroup of approximately 176 subjects at study sites qualified to perform the assessment of corneal endothelial cell parameters (endothelial cell density [cells/mm²], percent hexagonality and coefficient of variation). All eligible subjects at the participating study sites for corneal endothelial cell assessment will be requested to participate in the Sub-study. If a subject is unable or unwilling to participate in the Sub-study, the Investigator has the option to enroll the subject in the Main Study only (see [Section 4.4](#) for more details).

Subjects who experience postoperative inflammation on POD1 and who meet all other eligibility criteria will be randomized to one of two study treatments (either Treatment 1 or Treatment 2) at a 1:1 ratio:

- Treatment 1: 1 drop APP13007 BID (morning and evening) for 14 days instilled to the operated study eye
- Treatment 2: 1 drop matching vehicle placebo BID (morning and evening) for 14 days instilled to the operated study eye

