3.2.1 Study Visits and Assessments

Visit 1: Screening. Sign informed consent prior to the conduct of any study procedures or discontinuation of any medications related to this study. Screening will occur between 28 days to 1 day prior to cataract surgery. Review Inclusion and Exclusion criteria for eligibility.

Between Screening and the day of surgery (Day 0), the prospective subjects will be determined to be a suitable candidate for surgery during a pre-surgery medical assessment, where the routine medication list prescribed by the cataract surgeon should be reviewed to rule out prohibited medications (see [Section 5.4.2](#)).

Day 0/Day of Surgery: Subjects undergo routine cataract surgery via phacoemulsification and posterior chamber intraocular lens implantation according to the Investigator's normal procedures.

Visit 2: POD1 will occur ~ 18-34 h after cataract surgery. Review Inclusion and Exclusion criteria. Baseline pre-Randomization assessments (ocular inflammation, pain and safety assessments, and urine pregnancy test, if applicable). Randomization of eligible subjects. Instillation of first dose of study treatment in the operated study eye in the clinic under the supervision of Investigator or designee.

Visit 3: POD4 (\pm 1 day). Ocular inflammation, pain and safety assessments.

Visit 4: POD8 (\pm 1 day). Ocular inflammation, pain and safety assessments.

[Note: Subjects will be contacted on POD14 to remind them to stop study drug after that day and to bring the study drug bottle and dosing diary to the clinic the next day.]

Visit 5: POD15 (+ 1 day). Ocular inflammation, pain and safety assessments. Urine pregnancy test, if applicable.

Visit 6: POD22 (\pm 2 days). Ocular inflammation, pain and safety assessments. Final visit for the Main Study.

Subjects who are not participating in the Endothelial Cell sub-study will be discharged from the study after the assessments for Visit 6 (POD22) have been performed.

Additional Visits and Assessments for Subjects in the Endothelial Cell Sub-study at Qualified Study Sites

In addition to the visits and assessments in the Main Study described above, ~176 subjects consecutively randomized to APP13007 or placebo at the participating sites will have the following extra assessments/procedures:

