6.2.2 Day of Surgery (Day 0)

Prior to surgery, the surgeon's routine medication list should be reviewed to exclude prohibited medications (Table 4, [Section 5.4.2](#)). Surgery should preferably be scheduled in the morning to accommodate BID dosing on POD1. However, if surgery has to be scheduled in the afternoon, subjects should still instill two doses of study drug on POD1 at least 6 hours apart.

On Day 0, the surgeon will perform his/her routine cataract surgical procedure using phacoemulsification and implantation of a posterior chamber intraocular lens in the operated eye following the surgeon's usual pre-operative, operative, and post-operative procedures (with the exception of avoiding use of prohibited medications). Aqueous release procedures are not permitted.

Following surgery, the following should be performed:

- Give the subject instructions regarding routine post-surgical care and instructions regarding the use of concomitant medications and restricted medications during the study.
- Record surgery parameters in the source documents and eCRF.
 - For subjects in the Main Study (not in the Endothelial Cell Sub-study) record: surgery time, phacoemulsification information and the Surgeon evaluation of difficulty or complications.
 - For subjects in the Endothelial Cell sub-study record: Phacoemulsification machine make/model, Phacoemulsification time, Lens type, Cataract density grade and type, Location of wound, Coding of surgery as 'standard' or 'complex', Surgeon evaluation of difficulty or complications).
- Record the medications routinely administered for cataract surgery in the source documents. These medications will be reported as being used for routine cataract surgery.
- If a medication is administered due to an AE, the medication must be entered in the source documents, indicating that the medication was used to treat an AE.
- If a non-prostaglandin medication is used to lower IOP, the medication must be entered in the source documents and in the ConMeds page of the eCRF.
- AEs and ConMeds associated with an AE should only be recorded in the source document on Day 0 if they result in screen failure of the subject. If a subject is not a screen failure on Day 0, the AEs and ConMeds applicable to Day 0 should be recorded in the source documents when the subject returns for Visit 2 on POD1.

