
Safety Objective
 
The safety objective is to investigate the safety and tolerability of APP13007 versus matching vehicle placebo for the treatment of inflammation and pain after cataract surgery.
	
Safety Endpoints
 
• Adverse events (AEs)• Best corrected visual acuity by pinhole method using an ETDRS chart from baseline to each post-surgery visit• Slit-lamp biomicroscopy
○ Change-from-baseline in ocular signs to each post-surgery visit• Dilated indirect ophthalmoscopy
○ Change-from-baseline in ocular signs to Visit 6 (POD22)• Mean changes in corneal endothelial cell density, percent hexagonality and coefficient of variation from baseline (Visit 1/Screening) to Visit 7 (POD85) in the study eye in subjects in the Endothelial Cell Sub-study• Intraocular pressure (IOP) at each visit and change-from-baseline to Visit 6 (POD22) measured with a Goldmann applanation tonometer

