3. STUDY DESIGN

3.1 Study Design Overview

This Phase 3 study will evaluate APP13007 [REDACTED] in comparison to the matching vehicle placebo in a randomized, parallel-group, double-masked fashion. Subjects will have routine uncomplicated cataract surgery on Day 0 of the study and will be assessed the next day (POD1) after the surgery for eligibility for randomization to study treatment. The study comprises the Main Study and the Endothelial Cell Sub-study. All randomized subjects (approximately 370) will participate in the Main Study. The Endothelial Cell Sub-study will comprise a subgroup of approximately 176 subjects at study sites qualified to perform corneal endothelial cell parameter assessments.

All eligible subjects at the qualified study sites for corneal endothelial cell assessments will be requested to participate in the Sub-study. If a subject is unable or unwilling to participate in the Sub-study, the Investigator has the option to enroll the subject in the Main Study only, after consulting with the Study Medical Monitor.

Subjects who experience postoperative inflammation on POD1 and who meet all other eligibility criteria will be randomized, at a 1:1 ratio, to one of two study treatments (either Treatment 1 or Treatment 2):

[figure not shown]
- Treatment 1: 1 drop APP13007 twice daily (BID) (morning and evening) for 14 days instilled to the operated study eye
- Treatment 2: 1 drop matching vehicle placebo BID (morning and evening) for 14 days instilled to the operated study eye

After randomization, the first dose of study drug will be administered in the clinic on POD1 so that the site personnel can ensure the subject is able to administer the study drug correctly. The second drop of the study drug on POD1 will be administered by the subject a minimum of 6 hours later. For all other days, the first dose will be instilled in the morning and the second dose instilled a minimum of 6 hours, but preferably 8 to 12 hours, later. The number of drop(s) instilled and the date/time of instillation of each dose will be recorded by the subject in the subject's dosing diary. The study drug will be dosed BID for 14 days.

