8. DEMOGRAPHICS AND BASELINE CHARACTERISTICS

8.1 Demographics and Baseline Characteristics

Demographic data, including age, age category (< 65 or \geq 65 years), gender, race, ethnicity, iris color, study eye (OD or OS) will be summarized by treatment group and overall. In addition, a summary of the demographic data for the subjects in the Sub-study will be presented.

Demographic and baseline characteristics data, including the data collected on the surgery day (Day 0), will be listed in data listings. Data of contact lens use will be listed for the subjects in the Sub-study.

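### SAP 11.4 gives only within-arm endothelial change, which mixes surgical loss with any drug effect, and omits the between-arm POD85 difference that protocol 10.3.4 calls for.

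*SAP*

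**What the plan says.** **Baseline.** Protocol 3.2.1: "Screening will occur between 28 days to 1 day prior to cataract surgery". The SAP section 2 safety endpoint is mean change "from baseline (Visit 1/Screening) to Visit 7 (POD85) in the study eye in subjects in the Endothelial Cell Sub-study". The Schedule of Events has endothelial imaging at Screening, POD22 and POD85, with none between surgery and the first dose.

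**Randomization and dosing.** Protocol 3.1 says that subjects "will be assessed the next day (POD1) after uncomplicated surgery for eligibility for randomization to study treatment". SAP 3.1 says that they "will be randomized, at a 1:1 ratio, to one of two study treatments" and that "After randomization, the first dose of study drug will be administered in the clinic on POD1". SAP 6.4.5 stratifies randomization by site.

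**Analysis.** SAP 11.4: "The mean change from Screening to Visit 7/POD85 with associated 95% CI for the study eye will be tabulated for the three parameters", separately for each arm, plus percent change for cell density. It names no between-arm difference and no covariate. Protocol 10.3.4 asks for the mean change in each arm and also for the difference between arms with a 95% CI at POD85.

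**Covariates.** SAP 6.4.1 provides baseline adjustment only for the continuous secondary efficacy endpoints. SAP 10.2.2.2 analyses those by ANCOVA and presents an adjusted treatment difference with a 95% CI.

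**Surgical data.** Protocol 6.2.2 has Sub-study subjects' records include "Phacoemulsification machine make/model, Phacoemulsification time, Lens type, Cataract density grade and type, Location of wound", together with standard or complex coding and the surgeon's view of difficulty. SAP 8.1 says that demographic and baseline data, "including the data collected on the surgery day (Day 0), will be listed in data listings". Its by-arm summary covers demographics, iris color and study eye, but no surgical variable.

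**The concern.** The Sub-study exists to show whether APP13007 affects the corneal endothelium relative to vehicle. Phacoemulsification can itself cost endothelial cells, and that loss happens after the Screening image and before the first drop. A within-arm change from Screening to POD85 therefore cannot be read as a drug effect in either direction. A fall in the active arm could be wholly surgical.

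The comparison that answers the question is the one the SAP leaves out. If the SAP is followed as written, the report will put a confidence interval on the mixed quantity and none on the drug contrast. A contrast computed after unmasking would have an unspecified model. Nor would a by-arm table show whether the arms had similar operations.

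**Working it through.** **1. The plan's own figure.** Protocol 10.4 and SAP 4 take 80 per arm, allow 10% dropout, and enroll about 88 per arm.
- 80 × 1.10 = 88, the stated figure.
- 80 / (1 − 0.10) = 88.9, so 89.
- 88 × 0.90 = 79.2 evaluable.

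The stated number is reproduced to within one subject per arm. The 80 itself cannot be derived, because no SD, margin or power is given.

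**2. What each quantity contains.** Let S be the mean surgical loss and D the mean drug effect.
- Active arm, Screening to POD85: S + D.
- Vehicle arm: S.
- Active minus vehicle: D.

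S is the same in both arms in expectation, because allocation is made after surgery. The pre-surgery baseline does not bias the difference.

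**3. Illustration under assumed values.** 80 per arm, mean surgical loss 200 cells/mm², SD of change 200, surgical severity explaining 25% of the variance, 5,000 simulated trials:

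| True drug effect | Within-arm change, active | Between-arm difference (SE) | 95% CI coverage | Difference adjusted for severity (SE) |
|---|---|---|---|---|
| 0 | −200.5 | −0.7 (32.4) | 94.3% | −0.3 (28.0) |
| −50 | −249.5 | −49.5 (31.4) | 95.3% | −49.6 (27.2) |

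The within-arm figure moves with surgery. The difference recovers the drug effect with or without adjustment, and adjustment only reduces the SE.

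**4. Precision, in units of the SD of change (80 per arm).**
- Within-arm half-width: 1.96 / √80 = 0.22.
- Between-arm half-width, unadjusted: 1.96 × √(2/80) = 0.31.
- Adjusted: 0.31 × √(1 − R²).

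| Assumed R² | √(1 − R²) | Half-width | Narrowing | Equivalent n per arm, 80/(1 − R²) |
|---|---|---|---|---|
| 0.10 | 0.949 | 0.29 | 5% | 89 |
| 0.20 | 0.894 | 0.28 | 11% | 100 |
| 0.30 | 0.837 | 0.26 | 16% | 114 |
| 0.40 | 0.775 | 0.24 | 23% | 133 |

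**5. Chance imbalance.** The between-arm difference in a standardized surgical covariate has SE √(2/80) = 0.16. With R² = 0.25 (correlation 0.5), an imbalance of 1.96 SE (0.31) shifts the unadjusted difference by 0.31 × 0.5 = 0.155 SD, half of the 0.31 half-width.

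**The case against.** **The randomized comparison is sound.** A reader might infer that the pre-surgery baseline confounds the arm comparison, or that surgical covariates are needed to separate surgical loss from drug effect. The documents do not support that. Randomization on POD1 against concurrent vehicle balances prior surgical loss in expectation. This part of the objection stands in full.

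**The difference can be worked out by hand.** If n, mean and SD are tabulated by arm, the unadjusted difference and its interval follow. That is true and limits the harm. It does not hold for a baseline-adjusted difference, and it does not explain why the SAP drops an item that the protocol lists. Protocol 10.3.4 does qualify its list with an as-appropriate clause, but SAP 11.4 gives no reason for treating the comparison as inappropriate.

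**This is descriptive safety data.** No hypothesis, margin or power is attached, so a narrower interval changes no pre-specified decision. This stands, and it is why the surgical covariates are optional.

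**Chance imbalance is already in the interval.** An ordinary 95% CI allows for it, and the shift in step 5 lies inside the half-width. A reader might infer that an uneven mix of hard cataracts would pass for toxicity or hide it; the arithmetic does not show that. A by-arm table is still a useful check. About 10% dropout is expected and SAP 11 imputes no safety data, so the eyes imaged at POD85 are not exactly the randomized set.

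**The surgical variables are imperfect.** Protocol 6.2.2 records the machine make and model, so phacoemulsification times may not be comparable. Appendix B grades cataracts in the non-study eye only, and no density scale is given for the operated eye. Both points stand as conditions on using them. Protocol 6.2.2 also states no purpose for collecting them, and it records phacoemulsification information for Main Study subjects too. Neither an intended adjustment nor collection of phacoemulsification time in the Sub-study alone can be inferred.

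**Conclusion.** The point holds as an omission and a loss of precision. SAP 11.4 puts an interval only on within-arm change, which mixes surgery with drug, and omits the between-arm difference that protocol 10.3.4 lists. It also makes no use of the Screening value, although the SAP adjusts its continuous efficacy endpoints for baseline.

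The missing interval would have a half-width of about 0.31 SD of change with 80 evaluable eyes per arm. Adjustment would narrow it by about 5 to 23% if the covariates explain 10 to 40% of the variance. That range is an assumption, since the documents give neither an SD nor an R-squared, and exclusion of complicated or combined surgery may favor its lower end. Unbiasedness rests on randomization after surgery and on POD85 losses that do not disturb the balance between arms.

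**What to change.** 1. **SAP 11.4, main change.** For cell density, percent hexagonality and coefficient of variation, report the between-arm difference in change from Screening to POD85 with a 95% CI. Give it unadjusted, as protocol 10.3.4 states, and from an ANCOVA with treatment and the Screening value. Keep the within-arm summaries.
2. **SAP 11.4, optional.** Add phacoemulsification time and cataract density grade to the model, for precision only. Fix them before unmasking, and only once the grading scale and comparability across machines are confirmed.
3. **SAP 8.1.** Tabulate the Day 0 surgical variables by arm for the Sub-study, in addition to the listing.

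Cost: SAP wording, a few table shells and one model per parameter. No new procedures, visits or subjects. The downside is that a few subjects may lack a surgical covariate and drop out of the optional model; the unadjusted and Screening-adjusted results would not be affected.

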12. INTERIM ANALYSIS

No interim analyses are planned for this study.

